5.3.1 Secondary Efficacy Analysis

Summary statistics will be provided for each of the secondary efficacy variables. Change from baseline in log-transformed geometric mean IELTs and change from baseline in average mean IELTs will also be calculated and summarized.

Same ANCOVA model used in Section 5.2.1 will be used to the change from baseline in the log-transformed geometric mean IELT up to weeks 2, 4, 6, 8, and 10, respectively as well as change from baseline in interval-based log-transformed geometric mean IELT for weeks 4, 8

and 12, with treatment as the fixed effect, and log-transformed baseline geometric mean IELT as the covariate.

Summary statistics will be provided for average IELT as well as change from baseline in average IELT by timepoint. A similar ANCOVA model will be used on change from baseline in average IELT as well as the interval-based average IELTs: the model will have treatment as the fixed effect and the baseline average IELT as the covariate. Change from baseline in average IELTs up to weeks 2, 4, 6, 8, 10 and 12 and the interval-based change from baseline in average IELT for weeks 4, 8 and 12 will not be log-transformed prior to analyses.

5.3.2 Multiplicity Consideration among Secondary Efficacy Analyses

Not applicable

5.4 Other Analyses of Secondary Efficacy Variables

Nonparametric analysis using the Wilcoxon rank-sum test will be performed on the geometric mean IELT up to weeks 2, 4, 6, 8 and 10 as well as interval-based geometric mean IELT for weeks 4, 8 and 12, to compare each active BOTOX[®] dose level vs. placebo. Responder analyses described in 5.2.2 will also be carried out for geometric mean IELTs up to weeks 2, 4, 6, 8 and 10.

Treatment comparisons of each active BOTOX[®] dose level vs. placebo Geometric mean IELT up to weeks 4, 8 and 12 will also be performed using methods described in Zhou et al, 1997:

1. The likelihood-based Z-score test: the comparison between an active BOTOX[®] dose level *i* and placebo is evaluated by the statistic Z_i :

$$Z_{i} = \frac{\hat{\mu}_{i} - \hat{\mu}_{0} + \frac{1}{2}(S_{i}^{2} - S_{0}^{2})}{\sqrt{\frac{S_{i}^{2}}{n_{i}} + \frac{S_{0}^{2}}{n_{0}} + \frac{1}{2}(\frac{S_{i}^{4}}{n_{i} - 1} + \frac{S_{0}^{4}}{n_{0} - 1})}}$$

Where $\hat{\mu}_i$ and $\hat{\mu}_0$ are the sample mean of the log-transformed geometric mean IELT of dose level *i* and placebo, S_i^2 and S_0^2 are the sample variance of the log-transformed geometric mean IELT of dose level *i* and placebo, and n_i and n_0 are the sample size of dose level *i* and placebo, respectively.

Assuming that for each of the active dose level *i* and placebo, the geometric mean IELT are independently log-normally distributed with means M_i and M_0 , respectively, then Z_i tests the null hypothesis of $M_i=M_0$, and under the null hypothesis Z_i is approximately standard normal.

2. Bootstrap approach:

Let \overline{T}_i , \overline{T}_0 and $\overline{T}^{(i,0)}$ be the sample mean of the geometric mean IELT of the dose level i, placebo and the two groups combined, respectively. $T_k^{(i)} = T_{ik} - \overline{T}_i + \overline{T}^{(i,0)}$ and $T_j^{(0)} = T_{0j} - \overline{T}_0 + \overline{T}^{(i,0)}$ form a sample with common mean $\overline{T}^{(i,0)}$, where T_{ik} and T_{0j} are the geometric mean IELT for the kth patient in dose level i and the jth patient in the placebo group, for k=1, ..., n_i and j=1,..., n_0. Resample from them with replacement 2000 times, $Z_{i1}^{*(b)}$,..., $Z_{in_i}^{*(b)}$ and $Z_{01}^{*(b)}$,..., $Z_{0n_0}^{*(b)}$ for each b=1, ..., 2000. Compute

$$t_{b,i}^* = \frac{\overline{Z}_i^{*(b)} - \overline{Z}_0^{*(b)}}{\sqrt{\frac{\tau_i^{*(b)2}}{n_i} + \frac{\tau_0^{*(b)2}}{n_0}}}, \text{ for b=1,..., 2000.}$$

Where $\overline{Z}_i^{*(b)}$, $\tau_i^{*(b)2}$, $\overline{Z}_0^{*(b)}$, and $\tau_0^{*(b)2}$ are the sample mean and variance for the active does level *i* and placebo for the bth resample, respectively. The test statistic,

$$t_{obs,i} = \frac{\overline{T_i} - \overline{T_0}}{\sqrt{\frac{\hat{\tau}_i^2}{n_i} + \frac{\hat{\tau}_0^2}{n_0}}}$$

Where $\hat{\tau}_i^2$ and $\hat{\tau}_0^2$ are the sample variances of the observed geometric mean IELT of active dose level *i* and placebo, respectively.

Then the achieved significance level (ASL) for testing $H_0: M_i=M_0$ vs. $H_a: M_i \neq M_0$, for the dose level *i*, where M_i and M_0 are the means of the IELTs of dose level *i* and the placebo under the log-normal distribution, respectively.

$$\hat{ASL}_{i} = \frac{\# of \ times \mid t_{b,i}^{*} \mid \geq \mid t_{obx,i} \mid}{2000}$$

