7.5 Sample Size Calculation

For this exploratory study, an empirical sample size is used. For Cohorts 1-5, 8 patients will be randomized to receive BOTOX and 2 patients to placebo. In Cohort 6, 24 patients will be randomized in a 1:1 ratio. The power for detecting 2, 3 and 4-fold change (the ratio between groups) with differing values for the coefficient of variation (CV) assuming the IELT is log-normally distributed, using a 2-group t-test with a 1-sided 0.10 significance level are presented in Table 7–1. The CV assumption is estimated from the pooled analysis of week 12 data from Priligy (dapoxetine hydrochloride) film-coated tablets, 30 and 60 mg (Public Assessment Report Scientific Discussion of Priligy, 2008) (Table 7–2). The CV in the pivotal studies at week 12 ranges from 0.85 to 1.64. The commercial Guide 5.1 (procedure

Table 7–1 Power Calculation with Different Expected Fold-change Comparison Ratio and Coefficient of Variations

	BOTOX versus		
Expected Fold-change	Placebo	Coefficient of Variation	Power
		1	38%
2	8 versus 2	1.5	30%
		2	26%
	8 versus 8	1	63%
2		1.5	48%
		2	41%
		1	61%
3	8 versus 2	1.5	47%
		2	40%
3	8 versus 8	1	89%
		1.5	75%
		2	65%
4		1	76%
	8 versus 2	1.5	59%
		2	51%
4	8 versus 8	1	97%
		1.5	88%
		2	79%
		1	76%
2	12 versus 12	1.5	60%
		2	51%
		1	97%
3	12 versus 12	1.5	88%
		2	79%
		1	>99%
4	12 versus 12	1.5	96%
		2	91%

Table 7–2 Coefficient of Variation at Week 12 in Priligy Pivotal Studies

Study	Treatment Group	Mean (SD)	Coefficient of Variation
C-20052-012	Placebo	1.7 (2.09)	1.23
	DPX 30 mg PRN	2.9 (3.59)	1.24
	DPX 60mg PRN	3.4 (3.97)	1.17
C-2002-013	Placebo	1.8 (2.33)	1.29
	DPX 30 mg PRN	2.7 (3.39)	1.26
	DPX 60mg PRN	3.3 (3.40)	1.03
PRE-3001	Placebo	1.9 (3.11)	1.64
	DPX 30 mg PRN	3.2 (4.61)	1.44
	DPX 60mg PRN	3.5 (4.04)	1.15
PRE-3003	Placebo	2.4 (2.05)	0.85
	DPX 30 mg PRN	3.9 (3.95)	1.01
	DPX 60mg PRN	4.2 (3.97)	0.95
Pooled	Placebo	1.9 (2.43)	1.28
	DPX 30 mg PRN	3.1 (3.91)	1.26
	DPX 60mg PRN	3.6 (3.85)	1.07

DPX = dapoxetine hydrochloride; PRN = as needed; SD = standard deviation

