2.3 Data Conventions

- A one-sided, alpha=0.1 significance level will be used for this study for treatment comparisons, i.e., treatment differences are considered significant if the 1-sided p-value of the test used in the comparison is less than or equal to 0.1.
- Data will be pooled across centers in all analyses. Placebo patients from different cohorts will also be pooled to form the placebo treatment group in all analyses.
- Day 1 is defined as the day of the first study medication administration. Study day is calculated as: Study day=visit date-day 1 date +1 for visits occurred after day 1 and study=visit date -day 1 date for visits occurred before day 1.
- The Medical Dictionary for Regulatory Activities (MedDRA) will be used to code all adverse events and medical history.
- Medications will be coded by the World Health Organization Drug Dictionary Enhanced (WHO DDE) preferred name for the medication's name and MedDRA for the medication's indication.
- All adverse events/medications with missing onset/stop dates will be identified and the missing dates will be imputed as follows:
 - a) For adverse event onset date: if day and month are missing but year is available then the imputed date would be January 1st of that year, or day 1 if they are in the same year. If day is missing but month and year are available then the imputed day will be the first day of the month or day 1 if they are in the same month and year.
 - b) For adverse event stop date: if day and month are missing but year is available then the imputed day will be December 31st of that year, or the study exit date if they are in the same year. If only day is missing but moth and year are available then the imputed day will be the last day of the month of the year, or the study exit date if they are in the same month and year.

- Data from unscheduled/re-test visits, excluding lab data, will also be treated the same way as scheduled visits, i.e., put in the visit window and decided by the visit day's distance to target day as which one to be used in the analyses.
- Weight and height will be presented with the metric system units and laboratory data will be presented with the Standard International (SI) units.
- Summary statistics for continuous/ordinal data include sample size (N), mean, standard deviation, minimum, median, and maximum and that for categorical data include sample size (N), frequency count and percentage.

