5.2.2 Other Analyses of Primary Efficacy Variable(s)

As a sensitivity analysis to the log-normal assumption of the geometric mean IELT, Wilcoxon rank-sum test will be performed on the primary efficacy variable for the treatment difference for each of the active BOTOX[®] dose level vs. placebo.

In addition, responder analyses for the primary efficacy variable will also be performed. As treatment responder in PE are defined as 3-8 fold changes in geometric mean IELT, corresponding responders will be defined in the logarithmic value of a 3, 4, 5, 6, 7 and 8 fold

change (1.10, 1.39, 1.61, 1.79, 1.95, and 2.08, respectively) for the primary efficacy variable and the Pearson's chi-squared test will be used to compare the proportion of responders between each of the active BOTOX[®] dose group vs. placebo.

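### The SAP 5.4 Wilcoxon tests ignore baseline IELT, while the week-12 Wilcoxon in SAP 5.2.2 uses change from baseline, so the series is not comparable across weeks

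*SAP*

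**What the plan says.** **SAP 5.4.** "Nonparametric analysis using the Wilcoxon rank-sum test will be performed on the geometric mean IELT up to weeks 2, 4, 6, 8 and 10", and on the interval-based values for weeks 4, 8 and 12, each dose against placebo. The same section adds a likelihood-based Z-score test and a bootstrap test for weeks 4, 8 and 12. The Z-score inputs "are the sample mean of the log-transformed geometric mean IELT of dose level" *i* and of placebo, with the matching variances. The bootstrap resamples each patient's post-treatment geometric mean. None of the three has a baseline term.

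**SAP 5.2.2.** The "Wilcoxon rank-sum test will be performed on the primary efficacy variable". SAP 5.1 defines that variable as the change from baseline in log geometric mean IELT over the 12 weeks.

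**Where baseline is used.** SAP 2.1 admits to the mITT population only patients with both baseline and post-baseline IELT. SAP 5.2.1 (week 12) and SAP 5.3.1 (cumulative to weeks 2–10, and the three intervals) fit an ANCOVA with log baseline geometric mean IELT as covariate. The responder analyses, including those in SAP 5.4, use fold change from baseline.

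**The concern.** Two things look wrong.

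First, tests with one name answer different questions. Up to week 10, and in all three intervals including weeks 8–12, the Wilcoxon test compares post-treatment level. For the cumulative week-12 endpoint it compares change. A rise or fall in its p-value between week 10 and week 12 could reflect the switch rather than the drug. This needs no numerical assumption.

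Second, the SAP 5.4 tests set aside information held on every analysed patient. With 8 patients on a dose, chance baseline differences can be sizeable. If baseline predicts outcome, they pass into the unadjusted comparison and residual variation is larger than it need be. Where such a test disagrees with the ANCOVA, the reader cannot tell whether the distributional assumption or the missing baseline is responsible.

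**Working it through.** **Inputs from the documents**
- Significance level: "A one-sided, alpha=0.1 significance level will be used for this study for treatment comparisons" (SAP 2.3). Table 7–1 is computed "using a 2-group t-test with a 1-sided 0.10 significance level" (Protocol 7.5).
- Effect: "The power for detecting 2, 3 and 4-fold change (the ratio between groups"); I use 2-fold, ln 2 = 0.693.
- Spread: Table 7–1 uses CV 1, 1.5 and 2, and "The CV in the pivotal studies at week 12 ranges from 0.85 to 1.64". I use CV 1.5, so the log SD is σ = √ln(1 + 1.5²) = 1.086.
- Arms: "For Cohorts 1-5, 8 patients will be randomized to receive BOTOX and 2 patients to placebo", with 12 and 12 in Cohort 6. SAP 2.3 pools placebo, giving 5 × 2 + 12 = 22. The case examined is 8 versus 22, if all cohorts run, doses differ between cohorts and nobody is lost.

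**Assumptions, not in the documents**
- Correlation ρ between log baseline and log post-treatment IELT: 0 to 0.7.
- Ratio k of baseline log SD to post-treatment log SD: 0.5 or 1.

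**1. The plan's own figures.** Take the noncentral t with ncp = ln(fold) / (σ√(1/n₁ + 1/n₂)) and n₁ + n₂ − 2 df. At 2-fold and CV 1.5 this gives 30.3% (8 v 2), 48.3% (8 v 8) and 60.0% (12 v 12), against 30, 48 and 60% in Table 7–1. All 27 entries agree within 0.9 points. The table is itself an unadjusted two-group calculation and gives no power for the SAP 5.4 tests.

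**2. Chance imbalance on the outcome scale.** The SD of the between-arm baseline difference is √(1/8 + 1/22) = 0.413 baseline SDs. The part that reaches the outcome is ρ × 1.086 × 0.413 = 0.448ρ on the log scale, whatever the baseline SD:
- ρ = 0.3: exp(0.135) = 1.14-fold
- ρ = 0.5: exp(0.224) = 1.25-fold
- ρ = 0.7: exp(0.314) = 1.37-fold

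**3. Parametric guide to the power at stake.** Replacing σ by σ√(1 − ρ²) and removing one df, power at 8 v 22 goes from 59.6% unadjusted to 59.5, 62.3, 68.3 and 80.2% at ρ = 0, 0.3, 0.5 and 0.7.

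**4. Rank tests, simulated** (8 v 22, 2-fold, CV 1.5, one-sided 0.10; power in %):

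| ρ | Wilcoxon, post-treatment | Rank ANCOVA | Difference | Wilcoxon, change, k = 0.5 | Wilcoxon, change, k = 1 |
|---|---|---|---|---|---|
| 0 | 57 | 57 | 0 | 51 | 41 |
| 0.3 | 57 | 60 | 3 | 60 | 49 |
| 0.5 | 56 | 64 | 8 | 67 | 58 |
| 0.7 | 57 | 75 | 18 | 77 | 74 |

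The last two columns come from a separate simulation (20,000 runs per case). There, the Wilcoxon on post-treatment values gave about 58% throughout, and a Wilcoxon on baseline-adjusted residuals gave about 57, 60, 66 and 78%. The differences are therefore good to about two points, and adjusting costs at most about one point when baseline is uninformative.

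**5. Why simple change is not a full remedy.** The variance of change is σ²(1 + k² − 2kρ). It falls below σ² only if ρ > k/2, and it exceeds the adjusted variance σ²(1 − ρ²) by σ²(k − ρ)². With k = 0.5 and ρ of 0.3 or more, change does as well as adjustment in the table. With k = 1 and ρ = 0.3 it is worse than ignoring baseline (49% v 57%).

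**6. Test size.** With no treatment effect, the unadjusted Wilcoxon rejected in 9.3–10.6% of simulated trials, the Z-score test in 6.9–10.3% and the rank ANCOVA in 9–10%. The bootstrap test was not simulated.

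**The case against.** The case for leaving the plan alone is substantial. Every SAP 5.4 time point already has a baseline-adjusted ANCOVA. The trial is exploratory, without multiplicity control, and no decision rule rests on these tests. Protocol 7.3.2 itself names the Wilcoxon, Z-score and bootstrap tests on geometric mean IELT. The entry limits (screening mean of at most 1 minute, no qualifying event of 2 minutes or more) may lower the baseline correlation. All of this stands and limits the importance of the point. The last part is uncertain in direction: a zero event counts as 0.5 second, so four 50-second events give a geometric mean of 50, while two 50s and two zeros give (50² × 0.5²)^¼ = 5, a 10-fold difference within the entry limits.

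Four stronger readings are tempting and not supported:
- *All the supportive Wilcoxon tests ignore baseline.* The SAP 5.2.2 test uses change. It is also the only one the SAP presents as a check on log-normality.
- *The unadjusted tests give too many false positives.* Under randomization they do not (step 6). Pooling placebo over sequential cohorts makes early-dose comparisons not purely randomized, which is a further reason to adjust but not evidence of inflation.
- *Baseline imbalance can be set directly against the 2-fold effect.* With an assumed baseline log SD of 0.5–1.0, one SD of imbalance is 1.23- to 1.51-fold in baseline, but only the share in step 2 reaches the outcome.
- *The Z-score and bootstrap tests should be rebuilt on adjusted values.* They test equality of log-normal means, a different quantity; the protocol names them, and no calibration of an adjusted version is available.

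**Conclusion.** The point holds for the Wilcoxon tests in SAP 5.4. They make no use of a baseline available for every mITT patient, and they do not match the week-12 test in SAP 5.2.2. The inconsistency is certain from the text.

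The size of the loss is conditional. For 8 v 22, CV 1.5 and a 2-fold effect, it is about 0, 2–3, 8 and 18 power points at ρ = 0, 0.3, 0.5 and 0.7. A reader might infer that power is certainly lost, but that depends wholly on a correlation the documents do not give. The calculation also assumes log-normal values, complete cohorts and distinct doses. The primary result and the adjusted secondary ANCOVAs are untouched; what suffers is the precision and readability of supportive tests.

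**What to change.** - In SAP 5.4, use a rank ANCOVA (Quade) with baseline geometric mean IELT as covariate, each dose versus placebo, at every cumulative and interval time point.
- Report the same test at week 12 beside the SAP 5.2.2 Wilcoxon on change, so that one consistent series runs from week 2 to week 12. The change version alone is not enough, because it loses power when the correlation is low relative to the baseline SD.
- Keep the Z-score and bootstrap tests as specified, and label them in the SAP and the tables as unadjusted for baseline.

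Protocol 7.3.2 leaves its list of nonparametric methods open and defers details to the SAP, so there is room for the rank ANCOVA. If the sponsor prefers to retain the SAP 5.4 Wilcoxon because the protocol names it, show it alongside with the same unadjusted label. The cost is a few lines of SAP text and code; no new data are needed.

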5.6 Subgroup Analyses for Efficacy Variables

No subgroup analysis is planned.

6.1 Study Treatment – Exposure and Administration

6.1.1 Exposure to Study Treatment(s)

Patient exposure to the study medication will be characterized by study days. Study day is defined as the number of days from day 1 to exit; if the date of exit is missing, the date of the last visit will be used. Data will be summarized with descriptive statistics for each treatment group using safety population.

6.1.2 Administration of Study Treatment(s)

Patients will receive a single treatment administration during the study, consisting of 2 injections (each containing half of the total dose) of the assigned study medication to be delivered bilaterally (1 injection per side) to the bulbospongiosus muscle. Injection of the study medication will be performed using ultrasound guidance.

The following options are permitted either alone or in combination before treatment administration:

- No anesthesia
- Topical local anesthesia
 - Sterile local anesthetic topical preparation (eg, lidocaine cream) may be applied to the skin around the injection site
- Local anesthetic injections to skin
 - Sterile local anesthetic solution (eg, lidocaine solution) may be injected to the skin overlaying the injection site
- Sedation
 - If it is clinically indicated, may be administered to the patient at the investigator's discretion

Information on injection of study medication, including date, time of injection, number of injection sites, total volume injected and injection location will be provided in a data listing.

6.2 **Pre-Treatment Adverse Events**

Adverse Events with an onset date that is before day 1 of the randomized period of the study will be counted as pretreatment adverse events.

Adverse events will be coded from the verbatim text into MedDRA primary SOC and PT. Pretreatment AEs will be presented in descending order of incidence rate by the treatment group patient was randomized to for all randomized patients.

No statistical comparison will be performed.

A patient listing will be generated for pretreatment adverse events.

6.3 Pre-Treatment Serious Adverse Events

Pre-treatment serious adverse event will be collected and coded the same way as mentioned in Section 6.2 and a listing will be generated for pretreatment serious adverse events.

6.4 Adverse Events

AEs will be coded from the verbatim text into PT and the primary SOC using MedDRA.

AEs are collected both for the screening/baseline period pretreatment (which are referred to as pretreatment AEs) and for the follow-up period after treatment is initiated (which are referred to as posttreatment AEs). A treatment-emergent adverse event (TEAE) is an adverse event with onset on or after the initiation of study treatment or an adverse event with onset prior to study treatment that worsened in severity or became serious after the initiation of study treatment. For the randomized period of the study, TEAEs are those with onset on or after the first study treatment, and prior to the study treatment for the open-label period, if applicable; for the open-label period, TEAEs are those with onset on or after the study treatment for the open-label period.

Three incidence rate tables are standard for summarizing all TEAEs:

- by descending order of incidence rate
- by primary SOC and PT
- by primary SOC, PT and severity

Number and percent of patients with TEAEs will be tabulated by relationship to study drug and study procedures. All treatment-related TEAEs, either study drug-related or study procedure-related will also be presented by descending incidence and by primary SOC and PT for each treatment group. Separate tables will be generated for study drug-related and study procedure-related TEAEs. TEAEs leading to study discontinuation will also be tabulated by primary SOC and PT for each treatment group.

No statistical comparisons will be made for any adverse event table.

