Dose escalation will be based on the independent Data Review Committee (DRC) recommendation, following review of 4 weeks of safety and efficacy data from the preceding cohort. The DRC may also recommend to repeat cohorts, de-escalate the dose, assess alternative doses, or stop the study.

Based on the DRC recommendation for Cohort 6, patients will be enrolled in a 1:1 ratio of BOTOX placebo in the randomized period of the study and may elect to continue into the open-label period as described below. No stratification will be implemented.

Visit Schedule:

Cohorts 1 to 5:

- Screening period (washout if required will occur during the screening period)
- Day 1: Treatment visit
- Day 2: Follow-up telephone visit
- Week 1: Follow-up visit (telephone visit for nonsentinel patients, clinic visit for sentinel patients)
- Weeks 2, 4, and 8: Follow-up clinic visits
- Week 12: Clinic visit/study exit visit

Cohort 6 (Randomized Period):

- Screening period (washout if required will occur during the screening period)
- Day 1: Treatment visit
- Day 2: Follow-up telephone visit
- Week 1: Follow-up telephone visit
- Weeks 2, 4, and 8: Follow-up clinic visits
- Week 12: Clinic visit/study exit visit

Cohort 6 (Open-Label Period):

- Day 1: Treatment visit (may occur on the same day as the week 12 visit of the randomization period)
- Day 2: Follow-up telephone visit
- Week 2 and 8: Telephone follow-up visit
- Weeks 4 and 12: Follow-up clinic visit/study exit visit

[figure not shown]
Study Population Characteristics

Number of Patients: Based on the proposed doses it is anticipated that approximately 74 patients will be enrolled in the 6 planned cohorts. The actual number of patients entering the study will be determined by the number of cohorts (eg, escalations, repeat doses, de-escalations, or when the study is stopped). No more than 80 patients will be enrolled in the study.

Condition/Disease: premature ejaculation (PE)

Key Inclusion Criteria:

- written informed consent has been obtained from both the patient and his female partner
- male aged 18 to 60 years
- in a stable monogamous sexual relationship with a female partner for at least 6 months (with the intention to continue with the same partner for the duration of the study)
- diagnosed with lifelong PE (defined as symptoms starting at the time the patient became sexually active)

Key Exclusion Criteria:

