2.2 Clinical Hypotheses

BOTOX injected bilaterally into the bulbospongiosus muscle has an acceptable safety profile and shows an efficacy signal in comparison to placebo, as demonstrated by an increased IELT.

3. Study Design

This is a phase 2a, multicenter, randomized, double-blind, placebo-controlled, single treatment, pilot study followed by an open-label observation period, to assess a range of BOTOX doses for the treatment of male patients with PE. Patients will attend a minimum of 6 or 7 clinic visits and also have 1 or 2 telephone visits in the randomized period: screening, day 1 (treatment), day 2 (telephone visit for non-sentinel patients, clinic visit for sentinel patients, week 1 (telephone visit, and weeks 2, 4, 8, and 12/study exit). Partners will need to either attend a clinic visit or participate on a video conference during the screening period to provide informed consent and to receive training on measurement and recording of the IELT. For the open-label period, patients will have 2 clinic visits (weeks 4 and 12/study exit), along with 3 telephone visits (day 2, weeks 2, and 8).

For Cohorts 1-5, patients will be enrolled in cohorts of 10 patients. Within each cohort, 8 patients will receive BOTOX and 2 patients will receive placebo. For Cohort 6, patients will be enrolled into the randomized period in a 1:1 ratio, with 12 patients receiving BOTOX and 12 patients receiving placebo. Cohort 6 patients may choose to participate in the open-label period where they will receive BOTOX. For each treatment, patients will receive one injection of study medication delivered by ultrasound guidance bilaterally to the bulbospongiosus muscle.

Table 3–1 shows the planned dose escalation scheme; although, other interim doses may be recommended for investigation by the independent Data Review Committee (DRC) following data review.

Cohort	Total Dose	Sample Size	Total Patients in Cohort
1		N = 8	10
1	Placebo	N=2	10
2		N = 8	10
2	Placebo	N = 2	10
3		N = 8	10
	Placebo	N = 2	10
4		N = 8	10
	Placebo	N = 2	10
5		N = 8	10
	Placebo	N=2	10
6		N = 12	24
	Placebo	N = 12	24

Table 3–1 Planned Dose Escalation Scheme

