3.3 Open Label Period (Cohort 6)

At week 12, during the randomized period exit visit, patients who complete the double-blind period of the study will be eligible to enroll into the open-label period of the study.

The patient must complete the double-blind portion of the study and have received the first injection at least 12 weeks prior before receiving the second injection in the open-label period. Day 1 of the open-label period may occur on the same day as the week-12 visit of the randomized period (provided the 1st injection occurred at least 12 weeks prior) and may occur up to 4 weeks following the week-12 visit of the randomized period, provided all inclusion/exclusion criteria are met on the day of treatment.

If the Week 12 exit visit of the randomization period and the Day 1 treatment visit of the open-label period do not occur on the same day, the assessments of the Week 12 exit visit of

the randomization period should not be repeated at the Day 1 treatment visit of the open-label period, with the exception of recording AEs, concomitant medications/procedures, and vital signs.

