3.3.1 Qualification for Open-Label Period

To be able to enroll into the open-label period, the patient must meet these qualification criteria:

- 1. The patient must request to continue his participation and inclusion into the open-label period
- 2. The patient must complete the double-blind portion of the study and have received the first injection at least 12 weeks prior before receiving the second injection in the open-label period
- 3. The patient must be free of ejaculatory adverse events
- 4. The investigator deems that the open-label period treatment is medically appropriate and no condition or situation exists which, in the investigator's opinion, puts the patient at significant risk from receiving a second treatment

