3.3.2 Day 1 of Open-Label Period Injection

Day 1 of the open-label period may occur on the same day as the week-12 visit of the randomized period (provided the 1st injection occurred at least 12 weeks prior) and may occur up to 4 weeks following the week-12 visit of the randomized period, provided all inclusion/exclusion criteria continue to be met on the day of treatment. Week 12 exit assessments of the randomization period should not be repeated at the Day 1 treatment visit of the open-label period, with the exception of recording AEs, concomitant medications/procedures, and vital signs.

4. Study Population and Entry Criteria

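### The randomized-period TEAE window runs to the open-label injection for Cohort 6 continuers only, so the adverse event columns can cover unequal follow-up, with opposite effects for the Cohort 1-5 doses and the Cohort 6 dose

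*SAP*

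**What the plan says.** SAP 6.4 (Adverse Events) defines the randomized-period window thus: "TEAEs are those with onset on or after the first study treatment, and prior to the study treatment for the open-label period, if applicable". It writes no cap at week 12 or day 84. The summaries are numbers and percentages of patients by treatment group. No exposure-adjusted rate is described, and no between-group test is planned for any adverse event table. SAP 6.5 tabulates serious TEAEs, so the same definition carries over.

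Protocol 3.3 (Open Label Period) says that open-label Day 1 can coincide with the week-12 visit or "may occur up to 4 weeks following the week-12 visit of the randomized period". Protocol 3.3.2 says that week-12 assessments are not repeated on that day "with the exception of recording AEs, concomitant medications/procedures, and vital signs", so events that arise in the gap are collected. Protocol 3.3.1 lists the qualification criteria. The patient must ask to continue, and also: "The patient must be free of ejaculatory adverse events".

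Only Cohort 6 has an open-label period. For Cohorts 1 to 5, the visit schedule in the Protocol Summary ends with "Week 12: Clinic visit/study exit visit".

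Protocol Section 3 (Study Design) gives the arm sizes. For Cohorts 1-5: "Within each cohort, 8 patients will receive BOTOX and 2 patients will receive placebo". For Cohort 6: "with 12 patients receiving BOTOX and 12 patients receiving placebo". SAP 2.3 (Data Conventions) adds: "Placebo patients from different cohorts will also be pooled to form the placebo treatment group in all analyses".

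**The concern.** A crude percentage of patients with an event depends on how long they were watched. Under SAP 6.4 a Cohort 6 patient who continues can be watched for up to about 16 weeks within the randomized-period table. A Cohort 1-5 patient, or a Cohort 6 patient who does not continue, is watched for about 12 weeks. The shorter window comes from study exit, not from an SAP rule.

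Pooling turns this into a difference between columns. The placebo column mixes Cohort 1-5 patients, who cannot have the extra time, with Cohort 6 patients, who can. A Cohort 1-5 dose column has none of it. The Cohort 6 dose column can have it for every patient.

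The study sets out to explore safety over a range of doses. Its adverse event tables carry no tests and will be read by eye, so unequal windows can blur both the comparison with placebo and the comparison across doses.

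**Working it through.** **Inputs from the documents**
- Cohorts 1-5: 8 BOTOX and 2 placebo each. Cohort 6: 12 and 12 (Protocol Section 3). Check against Protocol 4.1: 5 × (8 + 2) + (12 + 12) = 74, the stated total.
- Pooled placebo (SAP 2.3): 5 × 2 + 12 = 22, of whom 12 (55%) are from Cohort 6.
- Randomized follow-up is 12 weeks. The gap g to the open-label injection is 0 to 4 weeks (Protocol 3.3).

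**Assumptions (not in the documents)**
- n of the 12 patients continue in each Cohort 6 arm, all with the same gap g.
- Everyone completes 12 weeks.
- The 12-week risk p of an event is the same in all groups (no drug effect), at a constant rate.
- The Cohort 6 dose has its own column. Doses are redacted, so this cannot be confirmed.

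**Step 1: mean follow-up per column**

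Placebo: (22 × 12 + n × g)/22. Cohort 6 dose: (12 × 12 + n × g)/12. Cohort 1-5 dose: 12.

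Maximum case (n = 12, g = 4):
- Placebo: (264 + 48)/22 = 14.18 weeks.
- Cohort 6 dose: (144 + 48)/12 = 16.00 weeks.
- Ratios: 14.18/12.00 = 1.18 (placebo to a Cohort 1-5 dose) and 16.00/14.18 = 1.13 (Cohort 6 dose to placebo).

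Half continuing with a 2-week gap (n = 6, g = 2):
- Placebo: (264 + 12)/22 = 12.55 weeks.
- Cohort 6 dose: (144 + 12)/12 = 13.00 weeks.

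With same-day injection (g = 0), every column is 12.00 weeks.

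**Step 2: spurious difference in percentages**

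Risk over 12 + g weeks: 1 - (1 - p)^((12 + g)/12).

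For p = 30%, g = 4: 1 - 0.7^(16/12) = 37.85%. For p = 30%, g = 2: 1 - 0.7^(14/12) = 34.04%.

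Maximum case at 30%:
- Placebo: (10 × 30 + 12 × 37.85)/22 = 34.28%.
- Cohort 1-5 dose minus placebo: 30.00 - 34.28 = -4.28 points.
- Cohort 6 dose minus placebo: 37.85 - 34.28 = +3.57 points.

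| Continuers per Cohort 6 arm, gap | Placebo | Cohort 1-5 dose minus placebo | Cohort 6 dose minus placebo |
|---|---|---|---|
| 12, 4 weeks | 34.3% | -4.3 | +3.6 |
| 6, 4 weeks | 32.1% | -2.1 | +1.8 |
| 6, 2 weeks | 31.1% | -1.1 | +0.9 |
| any, same day | 30.0% | 0 | 0 |

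In the maximum case, letting p run from 10% to 50% gives -1.7 to -5.6 points for Cohort 1-5 doses and +1.4 to +4.7 points for the Cohort 6 dose.

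**Step 3: in patients**

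The maximum case at 30% adds 12 × (0.3785 - 0.30) = 0.94 of a placebo patient with an event. For p from 10% to 50% the figure is about 0.4 to 1.2 patients.

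**Step 4: if the Cohort 6 dose repeats an earlier dose**

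SAP 2.1 analyses the safety population by dose received. An 8 + 12 column would average (8 × 12 + 12 × 16)/20 = 14.40 weeks in the maximum case, against 14.18 for placebo. At 30% the difference is (8 × 30 + 12 × 37.85)/20 - 34.28 = 34.71 - 34.28 = +0.43 points. For that dose the distortion nearly vanishes; for the other Cohort 1-5 doses it is unchanged.

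**The case against.** The strongest reply is that the effect is small and may not arise. The 4.3 points amount to less than one placebo patient, while one patient in an 8-patient dose column is 1/8 = 12.5 points. Same-day injection is expressly allowed. The stated duration of up to 24 weeks equals 12 + 12 and leaves no room for a gap; with the permitted gap it would be 12 + 4 + 12 = 28, so those passages need reconciling. A constant rate also gives no credit for events clustering soon after the procedure. All this stands and limits the size. It does not remove the unequal rule, because the 4-week gap is in the protocol and nothing in the SAP separates or adjusts for it.

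A second reply is that ending the window at the next injection assigns each event to the latest treatment, which is coherent. Protocol 1.5 expects an effect lasting several months, so a gap event may be a real effect of the first injection. This also stands. It argues against dropping gap events from the randomized-period display, and the fix keeps them.

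A reader might infer that the rule makes BOTOX look safer throughout. The documents do not support that. It holds for Cohort 1-5 doses against pooled placebo, but with equal uptake the Cohort 6 dose leans the other way.

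Nor does the requirement to be free of ejaculatory events show a direction. It applies to both Cohort 6 arms, and a man barred by such an event during the 12 weeks is already counted in that row. Only other event types could be under-collected, and which arm would continue more often is unknown.

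**Conclusion.** A minor but real point. Columns that will be read side by side can rest on different follow-up because of how SAP 6.4 closes the window and SAP 2.3 pools placebo. The 4-week excess belongs to a single continuer; the placebo column gains at most 2.18 weeks on average.

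At a 30% risk the largest distortion is about -4.3 points for Cohort 1-5 doses and +3.6 for the Cohort 6 dose. Both figures rest on assumed risk, uptake, gap length, constant rate and no drug effect, and the second also on the Cohort 6 dose not being grouped with an earlier one. Within Cohort 6 alone (12 against 12) the rule is the same for both arms, and equal uptake and gaps give equal follow-up. No test or decision rule is affected.

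**What to change.** In SAP 6.4, and for the serious TEAE tables in 6.5:

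- Make the between-group TEAE comparison on a common window for every patient: onset from the first treatment through the week-12 exit visit, or before the open-label injection if that is given the same day.
- Show events with onset between the week-12 visit and the open-label injection separately, by randomised arm.
- Keep the full-window table as a supplement, so that no late event is lost from the randomized-period display.

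Planned follow-up is then 12 weeks in every column of the comparison table. The ratios of 1.18 and 1.13 become 1.00, and the spurious differences become zero. The cost is a few lines of SAP text, one extra table and a listing. Data collection and trial conduct do not change.
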